## **An Open-Label Trial of Triheptanoin in Patients with Glucose Transporter Type-1 Deficiency Syndrome (GLUT1 DS)**

### **1.0 GOALS AND OBJECTIVES**

- 1.1 The primary objective of the study is:
- To evaluate the safety of triheptanoin via adverse event rates and laboratory values.
- 1.2 The secondary objective of the study is:
- To evaluate the long-term efficacy of triheptanoin as measured by the change in seizure frequency from historical baseline.

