## 5.4 Study Procedures

The dose will be ~35-40% of total caloric intake (~1-4 g/kg/day, depending on age), for up to 5 years, including the extension period, with a visit to the clinical site at day 1, Months 3, 6, 12, 18, 24, and annual thereafter for both groups. Enrolled subjects are otherwise able to maintain standard of care treatment which may include anti-epileptic drugs (AEDs) throughout the duration of the study.

Up to 50 patients with a diagnosis of GLUT1DS who have or have not been previously on Triheptanoin will be enrolled based on their prior treatment status.

During a two-week screening period, subjects will record daily seizures and diet (last three days) in a diary to serve as a baseline measurement. If a patient has recorded all screening criteria prior to consent, that data may be used in lieu of additional screening. If, in the opinion of the Investigator, a patient who is currently on the ketogenic diet would be placed at potential risk for compromise of patient safety by stopping ketogenic diet for two weeks before initiation of treatment protocol, the two-week screening period from consent to initiation may be waived by the Investigator. In the instance of waiving the screening period, seizure and diet information will be gathered retrospectively via parent/patient interview. After the Screening period, subjects will enter the treatment period on one of two protocol schedules. Study Visit window will be +/- 2 weeks from the scheduled date.

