#### 5.4.4 Assessment Schedules

##### 5.4.4.1 Diary

Beginning with the screening visit, subjects or caregivers will record daily seizure frequency and diet in the provided diary for 14 days and then during specified intervals. As such, subjects will record seizures and diet, as applicable, for 14 days post Visit 1 and for 14 days prior to each subsequent study visit.

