## 6.5 Tracking Diary

### 6.5.1 Seizures

A seizure diary will be used to track date, type, number, and unusual presentation of seizures. Subjects will be given a seizure diary at screening to record daily seizure activity for incremental periods of time. They will be instructed to record date and answer the question “Did you/your child experience any seizures today?” An affirmative answer requires completion of the form; a negative answer does not. Regardless of whether a subject experienced a seizure, additional medications administered and not previously recorded will be reported on this daily form. Subjects will describe activity during and post seizure. They will also record the type or description and number of other seizures that occurred that day.

Subjects will complete this form daily during the screening period. They will return the completed diary to the research team at Visit 1. Subjects will then receive a new seizure diary. Subjects will track daily seizures for two weeks following Visit one and then for two weeks prior to each subsequent study visit. Subjects will return the completed diary and receive a new diary at each visit.

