#### 11.2 *Efficacy Analysis*

For efficacy analysis, seizure frequency expressed as the number per month will be calculated during treatment and compared to the historical seizure rate prior to treatment with triheptanoin. Change from baseline will be expressed as median percent reduction in baseline seizure frequency.

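### The only efficacy figure is an uncontrolled median percent reduction with no interval, and if seizures cluster, 0% is not its expected value when the drug does nothing

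*Combined protocol and SAP*

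**What the plan says.** Section 11.2 contains the whole efficacy analysis. It states that "seizure frequency expressed as the number per month will be calculated during treatment", and that this rate is "compared to the historical seizure rate prior to treatment with triheptanoin". The summary is then fixed: "Change from baseline will be expressed as median percent reduction in baseline seizure frequency". No test, interval, model or reference value is given. Section 1.0 sets the secondary objective in matching terms, "as measured by the change in seizure frequency from historical baseline", and section 7.3 lists seizure frequency as the only efficacy measure. Section 3.0 describes an open-label study with no control arm.

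The on-treatment counts come from separate short diaries. Section 5.4.4.1 has them kept "for 14 days post Visit 1 and for 14 days prior to each subsequent study visit", and section 6.5.1 agrees.

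The baseline has more than one possible source. Sections 1.0 and 11.2 call it historical without giving a source or length. Section 5.4 says: "During a two-week screening period, subjects will record daily seizures and diet (last three days) in a diary to serve as a baseline measurement". Where screening is waived, "seizure and diet information will be gathered retrospectively via parent/patient interview". The plan does not say whether the on-treatment diaries are pooled or reported by visit, or what happens to a subject whose baseline count is zero.

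**The concern.** A reader will take a median reduction of 0% to mean no effect, and a positive median to mean benefit. With clustered seizures, most fortnights lie below a subject's own average and a few lie far above it. A subject's rate over a limited number of fortnights is therefore, typically, lower than that subject's long-run rate, and the median over subjects picks up this typical value. In a randomised comparison the same artefact would arise in both arms and largely cancel. Here nothing cancels it, and no interval shows how uncertain the figure is.

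The median also gives every subject equal weight, whether the on-treatment rate rests on 14 days or on 126. Shorter records are the more skewed ones.

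**Working it through.** The plan states no rate, dispersion, expected reduction or sample-size calculation, so there is no figure of its own to reproduce. The check is what the planned median does when the drug has no effect.

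**From the documents.** There are up to 50 subjects (section 3.2). There is one diary after Visit 1 and one before each of Visits 2 to 9: 1 + 8 = 9 diaries, and 9 × 14 = 126 days at most.

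**Assumed.** Each subject has a constant true rate, lognormal across subjects with log-SD 1 and a median of 1 to 30 per month. Fortnight counts are gamma-Poisson with variance μ + μ²/k, where a smaller k means more clustering. In the main runs 30% leave early, with 1 to 8 fortnights, and all of a subject's diaries are pooled.

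**Hand check at high rates, full diaries, historical rate known exactly.** Observed over true rate then behaves as a Gamma(9k) variable divided by its mean 9k. The median of Gamma(a) is about a − 1/3, so the apparent reduction is about (1/3)/(9k) = 1/(27k).

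| k | 1/(27k) | simulated, median rate 100 per 28 days |
|---|---|---|
| 2 | 1.9% | 1.8% |
| 1 | 3.7% | 3.6% |
| 0.5 | 7.4% | 6.9% |
| 0.3 | 12.3% | 11.7% |

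For one fortnight at k = 1 the median is ln 2, so the apparent reduction is 1 − 0.693 = 30.7%; the simulation also gives 30.7%. A subject seen for 14 days therefore has a typical no-effect reduction of about 31%, against about 4% for one seen for 126 days, yet each counts once.

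**Main runs, historical rate known exactly.** Average median reduction under no effect:

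- no clustering: about 0 to 5%
- k = 1: about 5 to 11%
- k = 0.5: about 10 to 16%, with a positive median in 86 to 90% of trials
- k = 0.2: about 22 to 30%

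**Changing only the baseline** (finite baseline count, zero baselines dropped, k from 1 to 0.2):

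| Baseline length | Shift under no effect |
|---|---|
| 26 to 52 weeks | positive throughout, roughly +4 to +31% |
| 12 weeks | about −4 to +30%, often near zero |
| 14 days | about −31 to +73% |

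**What drives the shift.** Skew alone is not enough. With two equal 14-day windows and every subject kept, a fall and a rise are equally likely (0.438 and 0.439 at a median rate of 10 per 28 days, k = 1) and the median is 0. Unequal window lengths create a shift, and so does dropping zero baselines. In that same equal-window case 20.5% of baselines are zero, and dropping them moves the median from 0 to about 30%. If results were reported visit by visit against a long-run rate, the shift would be +16 to +94% over k = 0.3 to 2 and median rates of 4 to 100.

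**The alternative estimate.** In the same kind of data, a pooled rate ratio and a subject-conditional Poisson rate ratio centred (log scale) at 0.98 to 1.04 in nearly every setting. They reached about 1.10 at k = 0.2 with a 14-day baseline. The mean of the individual ratios is not a safe substitute: with a 12-week baseline and k = 0.5 it averaged about 1.6.

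**The case against.** The strongest case against rests on four points.

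- **Direction.** A reader might infer that the plan's efficacy figure is biased toward benefit. The documents do not support that. They fix no baseline length, and the exactly known rate is a modelling convenience. With a 12-week baseline the shift largely vanishes at moderate clustering unless seizures are infrequent. With a 14-day baseline and a median of 30 seizures per month it is about −23% at k = 1, an apparent worsening. This objection stands. In partial reply, 11.2 names a historical rate before triheptanoin, and for Schedule A subjects still on the drug a screening diary cannot supply that.
- **Clustering and dropout.** Nothing in the documents says that seizures cluster, and the 30% early-leaving rate is assumed. Without clustering the shift is about 0 to 5% against a known rate. This stands, and is why a range is given.
- **Status.** This is a descriptive summary for a secondary objective, with no test or success threshold; safety is primary. That limits the weight of the point. It does not remove it, because this is the only efficacy result that will be read.
- **Feasibility.** A count model needs pre-triheptanoin counts and days. The plan does not secure these for previously treated subjects, or for those with interview data only. This stands and shapes the fix.

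**Conclusion.** The point holds as a statement about the reference value. If seizures cluster, 0% is not the expected value of the planned median when the drug does nothing, and the plan offers neither a control nor an interval to reveal this. Against a long-run historical average, about six months or more, the shift is toward apparent benefit: for an exactly known rate, roughly 0-5% with no clustering, 5-16% for k = 1 to 0.5, and 22-30% for k = 0.2. With a 12-week baseline it is often near zero; with a 14-day baseline it can be large and of either sign. A general bias toward benefit is not established, and skew by itself does not produce one. The sizes rest on the assumed rates, dispersion and dropout, and on pooling the diaries. This is a worthwhile, low-cost improvement to a secondary analysis, not a flaw in the primary safety objective.

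**What to change.** In section 11.2:

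1. Keep the median percent reduction, and state that 0% is not its no-effect value.
2. Beside it, report a within-subject rate ratio of on-treatment to pre-triheptanoin counts with a 95% CI. Take it from a log-link count model: Poisson GEE with robust variance, or negative binomial with a subject effect. Use log(observed days) as offset, so that a 14-day record no longer counts the same as a 126-day one.
3. Define one pre-triheptanoin baseline period and record its counts and days. List the subjects for whom these cannot be recovered: Schedule A subjects without a pre-drug diary, and subjects with waived screening and interview data only.

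The cost is SAP wording and one model, plus retrieval of pre-drug counts and days where they exist. The check used pooled and subject-conditional ratios; it did not fit the GEE or negative binomial model itself. The rate ratio is more sensitive than the median to subjects with very high counts, so both should be shown. Some subjects may drop out of the model for lack of baseline counts. The change does not remove regression to the mean, recall bias or time trends, which an uncontrolled design cannot separate from drug effect.

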### 12.0 HUMAN SUBJECTS

#### 12.1 *Institutional Review Board (IRB) Review and Informed Consent*

|   |  |
|---|--|
| Protocol Number: 2013-NEUR-001
Version: 4.1
23-Mar-2018 |  |
|---|--|

This protocol and the informed consent/assent documents and any subsequent modifications will be reviewed and approved by the CCHCS IRB. A signed consent form will be obtained from the LAR for each enrolled subject as described in detail in section 5.3.

*12.2 Study Modification/Discontinuation*

The study may be modified or discontinued at any time by the Cook Children's IRB, the sponsor, the OHRP, the FDA, or other government agencies as part of their duties to ensure that research subjects are protected.

|   |  |
|---|--|
| Protocol Number: 2013-NEUR-001
Version: 4.0
10-Jan-20184-Dec-2017 |  |
|---|--|

**TABLE 1: SCHEDULE OF EVENTS– SUBJECTS PREVIOUSLY ON AND CONTINUING ON TRIHEPTANOIN**

| Name of Visit   | Screening       | Initial Treatment |             |             |            | Extension | End of Study or Termination |
|---|-----------------|-------------------|-------------|-------------|------------|-----------|-----------------------------|
|   | Screening Visit | Visit 1           | Visit 2, 3  | Visits 4-6  | Visits 7-8 | Visit 9   |                             |
| Timepoint   | -14 days        | Day 1             | Week 13, 26 | Every 6 mos | Annually   | Annually  |                             |
| Informed Consent
a) LAR
b) Assent   | X               |                   |             |             |            |           |                             |
| Demographics  | X               |                   |             |             |            |           |                             |
| GLUT1 DS Medical History  | X   |                   |             |             |            |           |                             |
| Prior and Concomitant Medications & Therapies                                       | X               | X                 | X           | X           | X          | X         | X                           |
| Adverse Events  | X               | X                 | X           | X           | X          | X         | X                           |
| Dietician Consult 
(including 3-day diet record review)              |                 | X                 | X           | X           | X          | X         | X                           |
| Daily Patient Diary Review: Seizure Count   | X               | X                 | X           | X           | X          | X         | X                           |
| Weight and vitals   | X               | X                 | X           | X           | X          | X         | X                           |
| Physical Examination    | X               | X                 | X           | X           | X          | X         | X                           |
| Labs
a) CBC 
b) Chemistry                             | X               |                   | X           | X           | X          | X         | X                           |
| Vineland Adaptive Behavior Scales (Vineland-II)                                     | X               |                   | X           | X           | X          |           | X                           |
| Barry Albright Scale  | X               |                   | X           | X           | X          | X         | X                           |
| PedsQL  | X               |                   | X           | X           | X          |           | X                           |
| Columbia Suicide Severity Rating Scale (C-SSRS)                              | X               | X                 | X           | X           | X          | X         | X                           |
| Urinalysis: dipstick
To test for pregnancy in females of child-bearing potential | X               | X                 | X           |             |            |           |                             |

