## **4.0 SELECTION AND ENROLLMENT OF SUBJECTS**

### **4.1 Inclusion Criteria**

Individuals eligible to participate in this study must meet all of the following criteria:

- 1) Patients with GLUT1 DS by physician diagnosis
- 2) Males and females, aged 1 to 50 years
- 3) Allowed to be on concomitant AEDs
- 4) Patients are able to tolerate triheptanoin if they have been (or are currently being) treated with this medication
- 5) Must, in the opinion of the investigator, be willing and able to comply with study procedures and schedule
- 6) Provide written assent (if appropriate) and written informed consent by a Legally Authorized Representative (LAR) after the nature of the study has been explained, and prior to any research-related procedures
- 7) Sexually active subjects must be willing to use an acceptable method of contraception while participating in the study
- 8) Females of childbearing potential must have a negative pregnancy test at Screening and be willing to have additional pregnancy tests during the study

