### **4.2 Exclusion Criteria**

Individuals who meet any of the following exclusion criteria will not be eligible to participate in the study:

- 1) Patients and their Legally Authorized Representatives (as appropriate) not willing or able to give written or verbal assent or written informed consent.
- 2) Concomitant administration of a ketogenic diet for the treatment of GLUT1 deficiency at time of study drug initiation
- 3) Concomitant administration of valproic acid
- 4) In the Investigator's opinion, the patient may not be compliant
- 5) Pregnant or breastfeeding an infant at screening
- 6) Has a concurrent disease or condition, or laboratory abnormality that, in the view of the Investigator, places the subject at high risk for adverse events, or introduces additional safety concerns
- 7) History of or current suicidal ideation, behavior and attempts
- 8) Patient qualifies for any other clinical trial designed to progressively evaluate the safety and efficacy of triheptanoin as approved by the FDA under a separate IND which is open at Cook Children's

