#### 5.4.1 Schedule A

- Subjects previously treated with triheptanoin will continue to dose at approximately 35-40% of total daily calories (~1-4g/kg/day, depending on age).
- The visit schedule will be: Visit 1 (day 1), Visit 2 (13 weeks), Visit 3 (26 weeks), Visit 4 (52 weeks), Visit 5 (Year 2, week 26), Visit 6 (Year 2, Week 52), Visit 7 (end of Year 3), Visit 8 (end of Year 4), and Visit 9 (end of Year 5), with telephone follow-up between visits, as needed. (Table 1)

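### Scheduled pregnancy tests stop at Week 26 although dosing runs up to five years, and a girl who reaches childbearing potential after that has none scheduled

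*Combined protocol and SAP*

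**What the plan says.** In Table 1 the dipstick row, labelled "To test for pregnancy in females of child-bearing potential", is marked under Screening, Visit 1 and Visits 2-3 (Weeks 13 and 26). It is blank under Visits 4-6, Visits 7-8, Visit 9 and End of Study or Termination. Table 2, for subjects new to triheptanoin, shows the same pattern, and its Day 14 phone visit is also blank. Section 5.4.4.2 (Laboratory) lists blood tests only.

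Section 5.4 sets dosing "for up to 5 years, including the extension period". Section 5.4.1 places the later visits at "Visit 7 (end of Year 3), Visit 8 (end of Year 4), and Visit 9 (end of Year 5", with contact in between described as "with telephone follow-up between visits, as needed". Section 5.4.2 has the same late visits for Schedule B.

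On eligibility, Section 4.1 admits "Males and females, aged 1 to 50 years" and states: "Sexually active subjects must be willing to use an acceptable method of contraception while participating in the study". Criterion 8 of that section asks females of childbearing potential for a negative test at entry and to "be willing to have additional pregnancy tests during the study", without giving times. Section 4.2 excludes anyone "Pregnant or breastfeeding an infant at screening". Section 8.0 (removal criteria) does not mention pregnancy.

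**The concern.** The protocol treats pregnancy on drug as something to avoid: it excludes pregnancy at entry, asks sexually active subjects to use contraception throughout participation, and obtains agreement to further tests. Yet the scheduled check ends after six months of a treatment that can last five years, and the text gives no reason for stopping there.

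Girls who mature on study are the clearest case. A subject can enter as a young child, and nothing in the text calls for her childbearing potential to be looked at again. If she reaches it after Week 26, following the schedule exactly means she is never tested. A pregnancy could then be exposed to a drug supplying 35-40% of daily calories with no planned occasion to find it. What is at stake is protection of the subject and of a pregnancy. No estimate, error rate or sample-size figure depends on it.

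**Working it through.** **Inputs**

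- Marked dipstick columns: Screening, Day 1, Week 13, Week 26 (Tables 1 and 2).
- Visit times from Sections 5.4.1 and 5.4.2, taking a year as 52 weeks: Weeks 0, 13, 26, 52, 78, 104, 156, 208, 260.
- Maximum dosing: 5 years (Section 5.4) = 5 x 52 = 260 weeks.
- Visit window: plus or minus 2 weeks (Section 3.3).
- Planned enrolment: up to 50 (Section 3.2).

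**Are the blank cells real?** Two separate tables show the same blanks, and the C-SSRS row directly above the dipstick row is filled in every later column. A fault in reading the PDF is unlikely.

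**Schedule as written**

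- Scheduled tests: 4, the last at Week 26.
- Dosing time after the last test, for a five-year completer: 260 - 26 = 234 weeks; 234/260 = 90%.
- If Week 26 falls at the late edge of its window: 260 - 28 = 232 weeks; 232/260 = 89%.
- Site visits after Week 26 with no test: Weeks 52, 78, 104, 156, 208 and 260, that is 6 of the 9 numbered visits, plus the termination visit.
- For an earlier leaver the share is smaller. At Week 104, for example, (104 - 26)/104 = 75%.
- Girl reaching childbearing potential after Week 26: 0 scheduled tests.

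**Schedule with Visits 4-9 marked**

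| Interval (weeks) | Length |
|---|---|
| 26 to 52 | 26 |
| 52 to 78 | 26 |
| 78 to 104 | 26 |
| 104 to 156 | 52 |
| 156 to 208 | 52 |
| 208 to 260 | 52 |

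The lengths sum to 234. The longest is 52 weeks, or 52 + 2 + 2 = 56 if one visit is early and the next late. The three yearly gaps cover 3 x 52 = 156 of the 234 weeks (67%).

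**Extra tests**

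- Per eligible completer: 6, or 7 if Visit 9 and the termination visit are held separately.
- Ceiling if all 50 subjects were females of childbearing potential throughout: 6 x 50 = 300, or 7 x 50 = 350. The true number must be lower, because the trial enrols both sexes from age 1.
- Table 1 and Table 2 already mark CBC and chemistry at every one of these visits, so no visit is added.

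**The case against.** The strongest reply is that no consequence has been shown. The text describes no reproductive hazard, and Section 9.0 names gastrointestinal distress and weight gain as the commonest adverse effects. The number of females who could become pregnant cannot be derived and may be small. Nothing supplied supports one testing interval over another. All of that stands, and it limits the urgency.

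Other routes also exist. Criterion 8 allows a test at any time. Adverse events, weight and concomitant medication are reviewed at every site visit. The investigator can ask for a subject's removal (Section 8.0), and a congenital anomaly is a reportable SAE (Sections 10.6.1 and 10.6.4). None of these schedules or triggers a test. The physical examination is limited in the table footnotes to HEENT, neck and lungs. Section 7.2 lists GI disturbance and weight gain as drug reactions, so early signs of pregnancy could be put down to triheptanoin. The SAE route acts only after an adverse outcome.

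It is also fair to say that the remedy is partial. Each 52-week gap after Week 104 is longer than a pregnancy, and a test at Week 260 or at termination comes too late to limit exposure.

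A reader might infer more than the documents support:

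- **That the schedule contradicts criterion 8.** It does not. That criterion sets no times, and the tests at Day 1 and Weeks 13 and 26 satisfy its wording.
- **That 90% measures risk or missed pregnancies.** It is calendar time for a completer.
- **That contraception is required of everyone.** Section 4.1 limits it to sexually active subjects.
- **That the trial has no pregnancy-reporting rule.** The supplied text contains none, but the Investigator Brochure, the medical monitoring charter, the Data Dictionary, institutional policies and the consent pages were not available and may contain one.

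**Conclusion.** The point holds as a gap in the testing schedule. Pregnancy dipsticks are planned only to Week 26. A five-year completer then has about 234 of 260 weeks of dosing with no scheduled test, and a girl who matures after Week 26 has none at all. These figures rest on 52-week years, full five-year participation and the visit times in Section 5.4. The reading of the schedule is firm. The number of subjects concerned is unknown.

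The matter is one of participant protection and has no bearing on the safety summaries or the seizure analysis as planned. It deserves a change because the protocol already takes the precaution at entry and the remedy is cheap, not because harm has been shown.

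**What to change.** In Tables 1 and 2, mark the dipstick at Visits 4 to 9 and at early termination for females of childbearing potential, and add that childbearing potential is reassessed at each visit.

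**Cost.** A short amendment, and about six dipsticks per eligible completer (seven if Visit 9 and termination are separate), at visits where labs are already marked. Consent and assent wording must be checked for girls who mature on study, because criterion 8 sought agreement only from females already of childbearing potential. Testing adolescents can be sensitive and needs a considered procedure.

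**Remaining gap.** Yearly intervals persist after Week 104. Asking about pregnancy at any telephone or drug-resupply contact would help, but calls are made only when needed and shipment is at the pharmacy's option (Section 5.3), so this cannot replace a test.

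**Secondary suggestion.** If no other trial document covers it, state in Section 10.6 that an on-study pregnancy is reported and followed to outcome, and there or in Section 8.0 what a positive test leads to. Whether a pregnant subject stays on drug is a clinical decision for the sponsor.
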